12.4 STUDY DOCUMENTATION AND STORAGE

The investigator shall maintain a list of appropriately qualified persons to whom she has delegated trial duties. All persons authorized to make entries and/or corrections on case report forms will be included on the Delegation of Authority form.

The investigator and study staff are responsible for maintaining a comprehensive and centralized filing system of all study-related documentation. A subject's file should include:

- CRFs
- Informed consent documentation
- Source documentation

The study file should contain:

- The protocol and all amendments
- Current curriculum vitas of investigators
- Medical licenses of investigators
- The IRB statement of compliance and membership rosters
- Completed FDA form 1572
- All correspondence to and from the UAMS IRB, PRMC, and FDA.
- Any other study related documents

Study records will be retained on-site in accordance with applicable institutional and federal regulatory requirements.

12.5 STUDY REGISTRATION AND PUBLICATIONS

This clinical trial will be registered at ClinicalTrials.gov (www.clinicaltrials.gov), and information will be updated in a timely manner. The findings from this study will be presented at professional society meetings at national and international levels, and will be published in peer-reviewed journals.

14 APPENDIX

14.1 Appendix 1. Schedule of Study Assessments

	Within 60 days of Visit 1	Visits scheduled 3 wks (\pm 7 days) apart				6 months (\pm 2 wks) from Visit 4	6 months (\pm 2 wks) from 6-Month Visit	As soon as possible following 6-Month or 12-Month Visit	Additional Optional Follow-Up Visit(s)
	Screening Visit	Visit 1	Visit 2	Visit 3	Visit 4	6-Month Visit	12-Month Visit	Optional LEEP Visit	
Informed Consent	X								
Inclusion/ Exclusion Review	X								
Screening Visit Questionnaire	X								
Subject Contact Information	X								
History	X								
Physical Exam ^a	X					X	X		
Colposcopy ^{bc}	X					X	X		
ThinPrep sample ^d	X					X	X	X ^e	
Complete blood count (CBC) ^f	X	X		X		X	X	X ^g	X ^g
Comprehensive metabolic panel (CMP) ^h	X	X		X		X	X	X ^g	X ^g
Blood for Immunological Assessments ⁱ		X	X	X	X	X	X	X ^g	X ^g
Urine Pregnancy Test		X	X	X	X				
BMI		X							
Pre-Injection Vital Signs		X	X	X	X				
Vaccination		X	X	X	X				
Post-Injection Vital Signs		X	X	X	X				
Adverse Events		X	X	X	X	X	X	X	X
Concomitant Medications		X	X	X	X	X	X		
Analgesics offered		X	X	X	X				
Provide Subject Diary		X	X	X	X				
Collect Subject Diary ^j			X	X	X	X			
12-Month Visit Questionnaire							X		
Optional LEEP ^k								X	
Hysterectomy ^k						X	X	X	X
Visit Follow-up ^{l,m}	X							X	X ⁿ

^a Physical Examination will include blood pressure, heart rate, respiratory rate, body temperature, and body weight.

^b Colposcopy will include punch biopsy and endocervical curettage as indicated; biopsies will be obtained from all subjects at the 12-Month visit.

^c If performed in the OR, a COVID-19 test may be required per hospital policy prior to intervention. The study will pay for the mandatory pre-operative COVID-19 testing while institutional COVID-19 precautions are in effect.

^d Specimens will be collected for HPV-DNA and bacterial testing at Screening, 6- & 12-Month Visits. Pap smear added only at the 6-Month Visit.

^e This only needs to be collected when requested.

^f CBC will include white count, hemoglobin, hematocrit, and platelet counts.

^g These bloods draws only need to be done when requested.

^h CMP will include aspartate transaminase, alanine transaminase, albumin, alkaline phosphatase, total bilirubin, total protein, sodium, potassium, chloride, CO2, blood urea nitrogen (BUN), creatinine, calcium, and glucose

ⁱ Blood samples will be collected for ELISPOT assay, circulating immune cells, and/or other research laboratory assessments.

^j It is anticipated some participants in this population will not return completed diaries. However, there are mechanisms in place to collect this information. When this occurs staff will ask subjects whether they have experienced any adverse events or changes to concomitant medications and document their response in Epic. Missing diaries will not be considered protocol deviations.

^k In rare instances, should a diagnosis of invasive cervical cancer be confirmed, a hysterectomy may be offered if a study physician determines it to be medically necessary. This should be scheduled as soon as possible following the determination of medical necessity.

^l Test results and visit outcomes will be discussed with subjects via telephone. Optional follow-up visits may be scheduled to discuss test results, perform clinically indicated examinations/procedures, and/or further discuss a subject's condition. These should be scheduled as soon as possible.

^m Based on the results of the ELISPOT assay, some subjects will be furthered studied for cross-reactivity, epitope spreading, and/or defining novel T-cell epitopes.

ⁿ Other reasons for additional optional follow-up visits during study participation are referenced in section 6.11.

## IRB#202790 Phase II HSIL PepCan Trial Statistical Analysis Plan

# 8/4/23

## Overview

PepCan, the HPV therapeutic vaccine developed by our group, consists of 4 cGMP-grade synthetic peptides covering the HPV 16 E6 protein, along with *Candida* as a novel vaccine adjuvant. This combination is designed to boost anti-HPV E6 responses, which have been associated with clearance of HPV and regression of cervical lesions.  *Candida* is being used as a vaccine adjuvant because injections of recall antigen into common warts induces wart regression and anti-HPV T-cell responses.  *In vitro* studies showed that the vaccine's HPV 16 E6 peptides induce maturation of Langerhans cells, the main antigen-presenting cells in skin, and that *Candida* stimulates proliferation of T-cells. 

This is a Phase II randomized double-blind clinical trial for treatment of cervical intraepithelial neoplasia 2/3 (CIN2/3) with two treatment arms: PepCan and Candida. Because the Phase I results showed Th1 promotion and better clearance of non-HPV 16 infection compared to HPV 16 infection, a Candida-only arm was also included. The design of this clinical trial closely resembles the latest guidelines for treating young women with HSILs. 12 Potential study participants with recent Pap smear results that indicate HSILs or that cannot rule out HSILs are being recruited locally and widely through community-based efforts. The patient's eligibility for vaccination is assessed by explaining the inclusion and exclusion criteria, obtaining medical history (including a list of current medications), and performing a physical examination. The inclusion criteria are (1) women ages 18-50, (2) ability to provide informed consent, (3) willingness to comply with requirements of the protocol, and (4) recent Pap smear report of HSIL or "cannot rule out HSIL" or colposcopy-guided biopsy report of HSIL. The exclusion criteria are (1) history of disease or treatment that has caused immunosuppression, (2) pregnancy or attempting to be pregnant, (3) breast feeding, (4) allergy to Candida antigen, (5) history of severe asthma requiring emergency room visit or hospitalization <5 years, (6) history of invasive squamous cell carcinoma of the cervix, and (7) history of having received PepCan. Colposcopy with biopsy is then performed by a study gynecologist, and a ThinPrep sample for HPV-DNA testing is collected. A blood sample is drawn for a complete blood cell count (CBC; white blood cells [needs to be ≥3K], hemoglobin, hematocrit, platelets [≥50K]) and complete metabolic panel (CMP; ALT, AST, albumin, alkaline phosphatase, total bilirubin, total protein, sodium, potassium, chloride, CO2, BUN, creatinine, calcium, glucose). Subjects with biopsy-confirmed CIN2/3 then proceed to vaccination. The vaccine assignment is randomized to PepCan and Candida (1:1) and is double-blinded. Injections are given intradermally in limbs every 3 weeks, for a total of 4 injections. A urine pregnancy test is performed before each vaccination. CBC, CMP, and immunomonitoring are repeated during visits 1 and 3 and visits at 6 month and 12 month. PepCan is prepared by a research pharmacist by reconstituting lyophilized peptides with sterile water and drawing them in a syringe, along with 300 μL of Candida. Because PepCan and Candida are both colorless, no additional procedures are required for blinding. A nurse administers the vaccine intradermally in a limb. Any immediate AEs are recorded. Subjects are asked to record their symptoms in a diary. At the 6-month visit, colposcopy is performed and biopsies are taken if suspicious for progressing disease. ThinPrep sample for Papanicolaou smear and HPV testing is collected. If the disease is persistent or progressing, subjects would be provided an option to proceed to loop electrical excision procedure (LEEP). At 12-month visit, histological response is assessed by colposcopy-guided 4-quadrant biopsies. Results from each treatment arm will be compared to those from a historical placebo group. 13

The unblinding process can start when biopsy results are available for the last subject are available. However, research laboratory analyses will be ongoing for several months, so the laboratory personnel (including the PI) will be blinded until the last laboratory testing is complete (expected in May 2023).

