Diagnosis and Main Inclusion Criteria	Recent Pap smear result consistent with HSIL or “cannot rule out HSIL” or recent untreated colposcopy guided biopsy-confirmed HSIL
Eligibility for Vaccination	Recent untreated colposcopy guided biopsy-confirmed HSIL
Study Product(s), Dose, Route, Regimen	Test Article: Vaccine consisting of four HPV 16 E6 peptides in combination with Candin® (PepCan) or Candin® alone Route of Administration: Intradermal injection Peptide Dose Level: 50 µg/peptide/injection based on the clinically optimal dose from the Phase I study Candin® Dose Level: 300 µl/injection for PepCan and Candin® groups Dosing Regimen: 4 injections; three weeks between each injection Injection site: Limbs
Statistical Methodology	Clinical response data (PepCan or Candin®) will be compared to a historical placebo control group from a similarly designed clinical trial using appropriate statistical tests; measures of safety will be evaluated using descriptive statistics.

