1.5.14 Rationale for Randomization and Double-Blinding

In order to minimize bias, subjects who are eligible for vaccination will be randomly assigned to one of the two treatment arms (PepCan or Candin®) in a double-blinded fashion so the subjects and study staff (except for pharmacy staff) will not know which treatment is being administered. PepCan and Candin® are both clear solutions prepared in the same 1 mL syringe.

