3.1.2 Candin®

Candida Albicans Skin Test Antigen for Cellular Hypersensitivity will be supplied in the commercially marketed drug Candin®. The vials will be stored at 2°C to 8°C as directed by the package insert until use. This product is approved for multi-dosing. The dose of Candin® per injections for this study is 0.3 mL.

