3.1.3 Combining HPV Peptides and Candin®

Sterile water will be added to a vial containing the four cGMP peptides on the day of use. Reconstituted peptides will be drawn in a syringe depending on the dose level, and 0.3 mL of Candin® will be drawn into the same syringe. The combined peptide-Candin® mixture should be kept on ice or in refrigerator until immediately before injection.

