4.1 OVERVIEW

This is a single site Phase II clinical trial of PepCan for treating women with biopsy-proven HSILs randomized and double-blinded to two treatment arms. Half of the subjects will receive PepCan, and the other half will receive Candin® alone. The study design closely resembles the latest guidelines for treating young women with HSIL [14]. Study subjects will be patients attending the UAMS Obstetrics and Gynecology Clinics with untreated biopsy-proven HSILs and patients referred from other clinics. Four injections (one every 3 weeks) of PepCan or Candin® will be intradermally administered in the extremities. Clinical response will be assessed by comparison of colposcopy-guided biopsy results obtained prior to vaccination and at 12-Month Visit. Safety will be monitored from the time of enrollment through the 12-Month Visit. Blood will be drawn for laboratory testing and immunological analyses (“blood test”) prior to injection, after the second vaccination, 6 months after the fourth vaccination, and 12 months after the fourth vaccination. Blood will be drawn to aid T-cell analyses (“blood draw”) after the first and third vaccinations, and possibly at the Optional Follow-Up and/or Optional LEEP visits. HPV-DNA testing will be performed at Screening and 6- and 12-Month Visits (Fig. 6). If a subject has persistent HSIL at the 12-Month Visit or if a subject is withdrawn due to excessive toxicity, she will be given an option to return for a LEEP visit. Alternatively, she may choose to exit the study and be followed by a gynecologist for up to 2 years of observation as recommended before surgical treatment [14].

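### The SAP infers from equal colour that no further blinding step is needed, but as described the two syringes would differ in fill volume, which the blinded nurse could see

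*SAP*

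**What the plan says.** The blinding target is in protocol section 1.5.14: "the subjects and study staff (except for pharmacy staff) will not know which treatment is being administered". The same section gives the means: "PepCan and Candin® are both clear solutions prepared in the same 1 mL syringe". The SAP Overview goes further and closes the matter: "Because PepCan and Candida are both colorless, no additional procedures are required for blinding".

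The contents of the two syringes are described as follows.

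- **Candin, both arms.** The synopsis (section 1.1) gives "Candin® Dose Level: 300 µl/injection for PepCan and Candin® groups", and section 3.1.2 repeats that "The dose of Candin® per injections for this study is 0.3 mL".
- **PepCan.** The SAP describes "reconstituting lyophilized peptides with sterile water and drawing them in a syringe", together with 300 µL of Candida. Protocol section 3.1.3 says that after the peptides are drawn up, "0.3 mL of Candin® will be drawn into the same syringe".
- **Comparator.** Section 4.1 says "the other half will receive Candin® alone". No section describes how the comparator syringe is prepared.

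According to the SAP Overview, a nurse gives the injection. Only pharmacy staff are exempt from blinding.

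**The concern.** Section 1.5.14 and the SAP between them cover colour, clarity and syringe type. Neither covers fill volume, which is readily visible in a 1 mL syringe. The SAP does not merely omit a safeguard: it says that none is required. A site that follows the plan as written would therefore have no reason to add one.

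If fills differ, the protocol itself supplies the key: 0.3 mL means Candin, and more means PepCan. Two other provisions would make the pattern easier to read.

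- Section 1.6.4 has a study coordinator learn each woman's treatment as she completes or leaves, while others are still in the trial.
- Section 4.4 moves PepCan recipients to Candin if peptide supply fails. A nurse could then see the fill drop between visits, although the same section aims to keep treatment from the study team.

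At stake are the outcomes that depend on judgement or reporting. Adverse events are found partly by observation (section 10.2.2) and graded for relatedness (section 10.2.3). Common treatment-related events are then compared between arms by Fisher's exact test (SAP III.b). The relatedness judgement also feeds the discontinuation rule in section 4.3. The per-protocol set keeps only women who completed the 12-month assessment (SAP II.a), so arm-dependent exit could alter the denominators of PepCan versus Candin, the only randomised comparison.

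**Working it through.** The plan gives no fill volume for either arm, so there is no stated figure to reproduce. The check is volume arithmetic.

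**Inputs**

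- Candin per injection, both arms: 300 µL (protocol 1.1 and 3.1.2).
- Peptide per injection: 50 µg per peptide (protocol 3.2).
- Phase II reconstitution volume: not given (protocol 3.1.3 says only that sterile water is added).
- The only concentration in the documents: 550 µg per peptide in 770 µL, in the preclinical methods (protocol 1.3.3.3). Its use for Phase II is an assumption.

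**Direction**

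- PepCan fill = peptide volume + 300 µL.
- Comparator fill = 300 µL + any top-up.
- With no top-up, the difference equals the peptide volume, which is above zero whatever the reconstitution volume. The direction does not depend on the assumed concentration.

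**Size, for illustration**

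- Concentration = 550 / 770 = 0.714 µg/µL.
- Peptide volume = 50 / 0.714 = 70 µL.
- PepCan fill = 70 + 300 = 370 µL, against 300 µL. The ratio is 370 / 300 = 1.23, or 23% more.

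**Range over assumed peptide volumes**

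| Peptide volume (µL) | PepCan fill (µL) | Excess over 300 µL |
|---|---|---|
| 10 | 310 | 3% |
| 50 | 350 | 17% |
| 70 | 370 | 23% |
| 200 | 500 | 67% |
| 700 | 1000 | 233% |

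The last row fills a 1 mL syringe. At the low end the difference might pass unnoticed; over most of the range it would not.

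**Search for a safeguard.** Neither document mentions a diluent or vehicle in the Candin syringe, a matched fill, a sleeve or opaque barrel, or an injector who is allowed to be unblinded.

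**The case against.** The strongest reply is that a mismatch is inferred, not shown. The comparator's total fill is nowhere stated: 0.3 mL is the Candin dose, and the preparation text describes PepCan only. Section 3.1.1 gives preparation to the Research Pharmacy, whose own procedures are not in the documents and could include matching. This stands as a limit on certainty. It does not rescue the SAP sentence, which says that nothing beyond equal colour is required.

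The size is also open. Section 3.1.1 describes the Phase II vial differently from the preclinical one, so the 23% cannot be carried over. This stands too.

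A reader might infer that the woman herself can tell her arm from the fill. The documents do not support that. Under section 1.6.4 she receives the same agent at all four visits, so she normally has no second fill to compare, and nothing says that she is told what to expect. A supply interruption under section 4.4 is the exception, but it is contingent, and she would still need to know what the change meant. The plausible route is the nurse, who handles many syringes.

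A reader might also infer that the primary result is compromised. That goes too far. Two pathologists, blinded to each other's diagnosis, read the 12-month biopsies (section 6.9.1), and they are not described as handling syringes. Injections and follow-up examinations take place in different clinics (section 6.3). Two of the three primary comparisons are with a historical placebo group and do not depend on blinding between the two arms. The LEEP offer at 6 months turns on Pap or biopsy results, the woman's decision not to return and a physician's judgement (section 6.7.1), so a link from a syringe seen months earlier is possible but weak.

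**Conclusion.** The concern holds in a limited form. The SAP's conclusion does not follow from its premise: equal colour does not make the syringes indistinguishable. As described, the PepCan fill exceeds the comparator fill by the volume of peptide solution, provided that the comparator is not topped up. The nurse could then infer the arm. The amount is unknown; 0.37 against 0.30 mL is an illustration at the preclinical concentration.

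The exposure is chiefly in adverse event recording and relatedness, with a possible effect on early exit in the randomised comparison. Nothing in the documents shows that anyone was in fact unblinded. The point merits a correction because the plan rules out a safeguard that is cheap, and because the claim of double-blinding otherwise rests on colour, clarity and syringe type alone.

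**What to change.** 1. Replace the SAP sentence with a statement such as: *The research pharmacy dispenses both arms in syringes that cannot be told apart by colour, clarity or fill; the method and each arm's fill volume are given in protocol section 3.1.3.*
2. Amend section 3.1.3 to match. State the fill volume in each arm and how the syringes are made indistinguishable, by a masked barrel or a matched visible volume, without changing the amount of either product. A mask should hide the plunger position as well as the liquid. The choice between the two methods belongs to the sponsor and pharmacy.
3. If injections are already complete, which the SAP's date (8/4/23) and its expected end of laboratory testing (May 2023) suggest, report from pharmacy records the volumes actually dispensed in each arm. If they differed, disclose the limit on blinding alongside the adverse event comparison.

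The cost is one small pharmacy step and a few lines of text or, after the fact, a record check and a sentence in the report. No analysis changes, and no extra staff are needed.

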#### I. Baseline Characteristics

- a. Age, race, ethnicity, baseline histology, number of cervical quadrants involved, body mass index, serum albumin, serum total protein, receipt of HPV prophylactic vaccine, education level, parity, number of sexual partners, smoking, oral contraceptive use will be tabulated for the PepCan group, *Candida* group, and both combined.
- b. Welch's t-test will be used to compare age, number of cervical quadrants, and body mass index. Fisher's exact test will be used to compare remaining comparisons.

# III. Safety

- a. AEs are being assessed based on Common Terminology Criteria for Adverse Events (CTCAE) v 4.03 from the time of consent to the last study visit. They will be grouped separately into PepCan and *Candida* groups after unblinding.
- b. A table with commonly (recorded with ≥5% of injections) observed treatment-related AEs will be prepared. Comparisons of such AEs between the PepCan and Candida groups will be made using Fisher's exact test (two-sided).
- c. Another table with all AEs recorded will be created dividing them between the PepCan and *Candida* groups.

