6.2 STUDY VISIT WINDOWS

6.2.1 Between Visits of an Individual Subject

- The first vaccination visit (Visit 1) should be scheduled as soon as possible after all results from the screening visit are available, and subjects are deemed qualified to continue to the vaccination phase of the study, but no later than 60 days after the day punch biopsy was obtained (the screening day for most of the subjects).
- The subsequent vaccination visits (Visits 2-4) should be scheduled 3 weeks \pm 7 days apart.
- The 6-Month Visit should be scheduled 6 months \pm 2 weeks following Visit 4
- The 12-Month Visit should be scheduled 6 months \pm 2 weeks following 6-Month Visit.
- Optional LEEP visit (if subject chooses) should be scheduled as soon as possible after 12-Month Visit or after determining a subject needs to be withdrawn due to serious toxicity.

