9.2 ASSESSING SAFETY: SUMMARY OF ADVERSE EVENTS

Subjects who received at least one dose of PepCan or Candin® will be included in safety assessments. Results will be tabulated as shown in Table 2. The type of adverse reactions, the CTCAE grades, and whether the reactions are vaccine-related will be indicated.

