10.1 DEFINITIONS

10.1.1 Adverse Event

An adverse event is any occurrence or worsening of an undesirable or unintended sign, symptom, or disease that is temporally associated with the use of the vaccine, and it will be graded according to the Common Terminology Criteria for Adverse Events (CTCAE) Version 4.03. Local and/or systemic adverse events may include itching, burning, pain, peeling, rash, oozing, redness, tenderness, scarring, fever, nausea, dizziness, and wheezing. The subjects will be allowed to use and provided analgesics (such as ibuprofen or naproxen) according to the appropriate dosages after injections to limit any adverse events that may occur. Any adverse event will be reviewed and considered related or not related to the vaccine. All applicable events will be reported to the IRB according to IRB policy 10.2 and the FDA according to 21 CFR 312.32.

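### As written, SAP III.c would place adverse events from before the first injection in a PepCan or Candida column

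*SAP*

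**What the plan says.** SAP III.a assesses AEs "from the time of consent to the last study visit" and continues: "They will be grouped separately into PepCan and" Candida groups after unblinding. Two tables follow.

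- III.b: "A table with commonly (recorded with ≥5% of injections) observed treatment-related AEs will be prepared". Fisher's exact test compares the arms.
- III.c: "Another table with all AEs recorded will be created dividing them between the PepCan and" Candida groups. No test is planned.

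The SAP does not define a treatment-emergent event, set a first-injection cut or name a safety population. Protocol 9.2 supplies the population: "Subjects who received at least one dose of PepCan or Candin® will be included in safety assessments". That restricts the women, not the events. Section 9.2 also says that each reaction's relation to vaccine will be shown, in the layout of Table 2.

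On timing, protocol 6.2.1 asks for Visit 1 as soon as possible once screening results are in, "but no later than 60 days after the day punch biopsy was obtained (the screening day for most of the subjects").

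**The concern.** Consent is obtained at or before the Screening Visit (protocol 6.4.1). Between then and Visit 1 a woman may have colposcopy, punch biopsy, endocervical curettage and a first set of blood tests, all before any study product. An event in that period cannot be an effect of PepCan or Candin®, yet III.a and III.c read together would count it under one of them.

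Safety is the secondary objective and is to be described, not formally tested against a control (protocol 1.1). There is no concurrent untreated arm, so readers will take the absolute counts in each column as the safety record of each product. Randomisation makes pre-injection events similar in the two columns in expectation; it does not take them out of either. A relatedness mark labels such events but leaves them in the totals.

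The point concerns only the start of the window.

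**Working it through.** **Step 1: reproduce the plan's own figure.** The only stated figure that bears on the length of the window is the roughly 16 months per subject in protocol 5.3.

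- Biopsy to Visit 1, maximum: 60 days (6.2.1; Appendix 1 gives the same limit for screening).
- Visit 1 to Visit 4: 3 × 21 = 63 days (3.2).
- Visit 4 to the 12-Month Visit: 12 months = 365.25 days (6.2.1).
- Total: 60 + 63 + 365.25 = 488.25 days. Divided by 30.4375 days per month, this is 16.04 months, which matches.

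**Step 2: share of the window before any injection.** Share = g / (g + 63 + 365.25), where g is the gap in days. Only the 60-day value comes from the documents; the others are assumed.

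| Gap g (days) | Share of window |
|---|---|
| 14 (assumed) | 3.2% |
| 30 (assumed) | 6.5% |
| 45 (assumed) | 9.5% |
| 60 (cap) | 12.3% |

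At the cap, the visit windows (±7 days for each of three injection intervals, ±2 weeks for each of two six-month intervals) move the share between 60/537.25 = 11.2% and 60/439.25 = 13.7%.

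The 60 days run from the biopsy, not from consent. The gap from consent is usually shorter for a woman who consents after an outside biopsy, which need not be repeated (6.4.1). It can be slightly longer if consent was signed before the Screening Visit.

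**Step 3: does the protocol settle when the window opens?** It does not.

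| Points to inclusion | Points to exclusion |
|---|---|
| SAP III.a: from consent | 10.1.1: an AE is one "that is temporally associated with the use of the vaccine" |
| Protocol 2.2, 4.1 and 10.2.1: from enrollment | Appendix 1: the AE row is blank at Screening and starts at Visit 1 |
| Protocol 5.2: women are enrolled for screening, so enrollment precedes vaccination | 6.5.1: the diary is first handed out at Visit 1 |

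**Step 4: effect on each table.** Let a and b be the post-injection event counts in the two arms, and c the expected pre-injection count in each, taken as equal under 1:1 randomisation.

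- Column totals become a + c and b + c, so both are inflated.
- Difference: (a + c) − (b + c) = a − b, unchanged in expectation.
- Ratio: (a + c)/(b + c) lies closer to 1 than a/b whenever c > 0 and a ≠ b.
- The observed pre-injection counts will not be exactly equal with about 40 women per arm, so the difference also gains chance noise.
- III.b is limited to treatment-related events. An event before the first injection should not be judged treatment-related, so III.b is essentially untouched.

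Equal c is not assured if the interruption rule in protocol 4.4 is used, because women who start during an interruption go to Candin® without randomisation.

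**Step 5: number of events.** This cannot be computed. Table 2 of the protocol lists event types that could arise before injection (anemia, neutropenia, hypokalemia, abnormal uterine bleeding, vaginal infection), but it gives no onset relative to consent or first dose.

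**The case against.** The strongest reply is that the protocol already excludes these events. If an AE must be temporally associated with vaccine use, an event before any injection is not an AE and cannot be among those recorded. The schedule and the diary, both starting at Visit 1, fit that reading. This stands far enough that one cannot say pre-injection events will certainly be tabulated by arm. It does not close the matter, because three protocol sections and the SAP open the window at enrollment or consent, and III.c takes everything recorded.

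A second reply is that little is exposed. III.b, the only safety table with a test, is limited to treatment-related events, and III.c does not claim to show post-treatment events only. Section 9.2 marks relatedness, and Table 2 footnotes unrelated events with counts, so a careful reader could separate those judged unrelated. This is largely right and limits the point to the totals in III.c.

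A third reply is that 12% overstates the matter. That also stands. It is a share of calendar days at the cap. Injection-site reactions, the most common events in Phase I (protocol 1.4.3), cannot occur before an injection, and no diary covers the period, so the share of events may be well below 12%.

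**Conclusion.** The point holds in a limited form. As written, SAP III.a and III.c would place an event recorded between consent and first injection in a dosed woman under an arm, and no other text in either document clearly removes it. The period is at most 60 days from biopsy, about 12% of a 488-day window at the cap and 6.5% for an assumed 30-day gap. The per-arm counts in III.c are inflated by an unknown number, ratios are diluted, and some noise is added.

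A reader might infer three stronger things that the documents do not support:

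- That about 12% of the tabulated events are misplaced. No pre-injection event rate is given.
- That the safety comparison between arms is biased. The expected difference in counts is unchanged under randomisation, and the tested table is restricted to treatment-related events.
- That every screened woman's events are involved. Protocol 5.2 plans 125 screened and 80 vaccinated; the other 45 fall outside the section 9.2 population.

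The conclusion assumes that some pre-injection events are in fact recorded, which the conflicting protocol sections leave open. It is a low-priority improvement that costs little.

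**What to change.** Replace SAP III.c with wording such as:

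> For women who received at least one injection, a table by arm will show all AEs that start or worsen after the first injection. AEs from consent to the first injection in these women will be listed separately, without arm. For laboratory events, baseline is the last value obtained before the first injection.

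Leave III.b as it is. Naming one laboratory baseline matters because blood counts and metabolic panels are drawn both at Screening and at Visit 1, where the draw is listed before the injection (protocol 6.4.1 and 6.5.1), and the two may differ.

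Separately, reconcile protocol 2.2, 4.1 and 10.2.1 with 10.1.1 and the AE row of Appendix 1, so that the start of AE collection is stated once. A collection period that opens at consent is compatible with a by-arm table that opens at the first injection, provided both are stated.

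The cost is one derived flag and one extra listing. The flag assumes that AE onset is recorded with enough detail to place it before or after the first injection. The documents give some support: the Table 2 footnotes classify Phase I reactions by hours from vaccination, and protocol 1.5.10 says safety will be assessed in the same manner here. No events are lost, because the earlier ones remain in the listing.
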